7.4. Specific Restrictions / Requirements

Not applicable.

#UTHealth Houston

7.5. Blinding

The investigators evaluating the primary and secondary outcomes will be blinded to the group assignments. The study participants, pharmacists, physicians and nurses taking care of the patients will not be blinded.

8. SAFETY MEASUREMENTS

Any adverse events encountered will be documented in the patients' chart once it is noted. These include QTc >500, high grade arrhythmias such as ventricular tachycardia, hypotension and elevated Liver function testing more than 2.5 times the upper limit of normal.

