3.4. Exclusion Criteria

All subjects meeting any of the exclusion criteria at baseline will be excluded from participation.

- 1. Patients with history of opioid drug abuse
- 2. Patients receiving schedule II narcotics on a chronic basis for longer than 6 months prior to ICU admission or on other analgesic infusions other than Fentanyl or Hydromorphone
- 3. Patients with cervical spinal cord injury or neuromuscular disease
- 4. Patients with end stage liver disease at ICU admission (ie, International normalized ratio ≥2and not taking warfarin and/or a total serum bilirubin ≥1.5 times above normal limits
- 5. Patients with prolonged QTc interval ≥500
- 6. Patients with prior history of cardiac conduction defects or suddendeath
- 7. Patients with QTc increase of ≥60 milliseconds above the value of prior EKGs measured during current ICU admission
- 8. Patients with more than 5 days on IV analgesia
- 9. Patients intubated for more than 30 days
- 10. Patients without feeding tubes
- 11. Patients not receiving enteral feeding
- 12. Exclusion of patients in a comatose state
- 13. Exclusion of patients in Status Epilepticus
- 14. Exclusion of post-operative patients

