5. STUDY DESIGN

5.1. Summary of Study Design

The study is randomized clinical trial. The duration of the study is 2 years. Patients will be screened to confirm they meet study criteria. Consent will be obtained from the legal authorized representative. Initial demographic data will be obtained using REDCap Database. Patients will be randomized to either Oral Methadone tablets or Non-Methadone group. The control group will receive usual care with IV Fentanyl or hydromorphone per hospital protocols as on appendix 1. Patients on the methadone group will be started on Methadone 5mg, 10mg or 15mg every 8 hours depending on Fentanyl drip rate (0-100mcg/hr, 100-200mcg/hr or >200mcg/hr) or hydromorphone drip rate (0-1.5mg/hr, 1.5-3mg/hr, or >3mg/hr). The rate of Fentanyl or hydromorphone will be reduced by 25% initially. If patients require additional sedation later, this will be administered per usual care and the total amount of additional opioids will be documented and used for analysis as morphine milligram equivalents (MME). Likewise, patients could be weaned more than 25% if they showed signs of tolerance to lesser sedation.

At Subsequent encounters: Rate of Fentanyl or Hydromorphone drip will be reduced by 25% every 24 hours until the patient is extubated from the ventilator.

Continuous IV opioids for analgesia for patients on mechanical ventilation is routine clinical care and will not be denied to patients. Once patients are extubated oral methadone will be discontinued and patient monitored for any opioid withdrawal symptoms and treated per protocol as shown on appendix 2 based on their clinical opiate withdrawal scale (COWS) appendix 4. For those with a score of less than 25 oral methadone will no longer be required. For those with a COWS score of >25 methadone will be resumed for a short taper of 3 days. The above can be illustrated as on study protocol flow on Appendix 5 and details on methadone taper as on Appendix 2.

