6. METHODS AND ASSESSMENTS

Based on the assumptions of successful extubation by day 5 of 50% of patients in the methadone group and 20% of patients in the control group and using a two tailed alpha level of 5%, a power of 80% our sample size calculation comparing proportions of two groups yielded 76. A 5% fallout as correction factor was 4 leaving us with a sample size of 80 patients. Statistical methods will include descriptive statistics and time to event analysis. Baseline characteristics will be reported. Data will be collected on a data collection sheet prior to transfer to REDCAPs database (Appendix 6). We will generate Kaplan-Meier curves and for comparison of hazard between groups we will use Cox regression (Cox proportional hazards model). Patients who die will be censored at time of death. Time of weaning will take into consideration only patients who were permanently disconnected from the ventilator. QTc values will be obtained from patient monitors and documented on data collection tool daily.

Randomization tables will be generated using REDCAPs database by study statistician. At the end of the study recorded information from REDCAPs will be exported to STATA for statistical analysis.

#UTHealth Houston

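### Section 5.1 gives methadone every 8 hours until extubation, and no readable text states a QTc value at which a dose is held, although QTc is read daily and the same limits bar entry

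*Combined protocol and SAP*

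**What the plan says.** Dosing is set in Section 5.1: "Patients on the methadone group will be started on Methadone 5mg, 10mg or 15mg every 8 hours depending on Fentanyl drip rate". The same section names one stop for the drug: "Once patients are extubated oral methadone will be discontinued". Section 4.2 also ends participation at ICU discharge, death, comfort care or 30 days. None of these depends on QTc.

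Section 3.4 has two QTc bars to entry: "Patients with prolonged QTc interval ≥500" and "Patients with QTc increase of ≥60 milliseconds above the value of prior EKGs measured during current ICU admission".

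Section 6 provides the on-treatment measurement: "QTc values will be obtained from patient monitors and documented on data collection tool daily". A 12-lead EKG is scheduled only at baseline and, for patients still on methadone, at day 30 (Section 4.2).

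Section 8 gives the response: "Any adverse events encountered will be documented in the patients' chart once it is noted. These include QTc >500".

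If a methadone patient needs more opioid, Section 5.1 already has a route: "If patients require additional sedation later, this will be administered per usual care and the total amount of additional opioids will be documented". The amount is expressed in MME.

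**The concern.** The trial has the daily measurement and has chosen its limits, but the readable text does not connect them to the drug. A patient whose QTc reaches 500 ms on day 2 of methadone could not have been enrolled that day, yet neither Section 5.1 nor Section 8 says what happens to the next dose.

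Two things are at stake. The first is safety: methadone prolongs the QT interval, and the attached label carries a boxed warning on it. The second is interpretation. The treating team is unblinded (Section 6.1), so without a rule each clinician decides whether to hold. A hold comes after a crossing, so it does not change whether a patient ever crosses. It does change later methadone exposure, how long QTc stays prolonged, and the highest and mean values. Prolonged QTc after methadone is a named secondary outcome (Section 2.5), so these quantities should not rest on unstated local practice.

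**Working it through.** The plan has no figure of its own to reproduce here, so the check is mainly textual. Each readable place where a hold rule could stand was read for two things: an on-treatment QTc value, and a dose action tied to it.

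| Place | Content on QTc | Value? | Dose action? |
|---|---|---|---|
| 3.4 | Bars entry at 500 or more, or a rise of 60 ms or more | Yes, at entry only | Not enrolled |
| 3.5 | Stopping the study; nothing on one patient's drug | No | No |
| 5.1 | Dose every 8 h, stop at extubation | No | No |
| 6 | Daily reading from monitors | No | No |
| 7.3 | Warns against use in QT prolongation | No | General warning, no hold or restart step |
| 7.4 | Specific restrictions: marked as not applicable | No | No |
| 8 | Values above 500 are charted | Yes | No |
| 8.1 | Persistent prolongation is a serious event | No | No |
| 8.2 | Event goes to the principal investigator for causality and expectedness | No | No |
| Safety Monitoring Plan | Quarterly team and DSMB review | No | No |
| Appendix 2 | Monitor QTc | No | No |
| Appendix 3 (label), 2.5 and 5.4 | Doses may be reduced for unacceptable reactions; look for modifiable risk factors | No | Advisory only |

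Section 8 is the only place with an on-treatment value, and its action is charting.

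The limits also do not line up. A rise from 430 to 490 ms is 490 − 430 = 60 ms. It bars entry but stays below the value that Section 8 names.

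**Exposure between readings.** The inputs are the 8-hour interval and the 5, 10 or 15 mg doses (Section 5.1), the daily reading (Section 6) and the 30-day limit (Section 4.2).
- Doses per reading interval: 24 / 8 = 3.
- Amount: 3 × 5, 3 × 10 or 3 × 15 = 15, 30 or 45 mg.
- Most doses possible in the trial at this interval: 3 × 30 = 90.

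**Chance that the trial meets the situation.** With 80 patients randomized 1 to 1, 80 / 2 = 40 receive methadone. The documents give no rate of crossing a limit, so the rate p is an assumption, with patients taken as independent. P(at least one) = 1 − (1 − p)^40.

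| Assumed p | P(at least one of 40) |
|---|---|
| 1% | 33% |
| 2.5% | 64% |
| 5% | 87% |
| 10% | 98.5% |

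These are chances of a crossing from any cause, not of harm and not of an excess due to methadone.

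**Recording.** The readable QTc field in Appendix 6 is the mean while on methadone. Two readings of 430 and 500 average (430 + 500) / 2 = 465, so the mean can hide the reading that matters.

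**The case against.** The strongest reply is Section 7.3. It stands under study drug administration, it lists QT prolongation among the reasons not to use methadone, and it is not confined to entry. A reader might infer from Sections 5.1 and 8 that the protocol directs staff to dose through a prolonged QTc. Section 7.3 does not support that reading, and clinicians remain free to hold a dose on judgement. What is missing is narrower: a value, an action and a restart condition.

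The safety system is also fuller than the one sentence in Section 8. Section 8.1 makes persistent prolongation serious, Section 8.2 brings every identified event to the principal investigator, and the list in Section 8 is not exhaustive, so a 60 ms rise could still be recorded. Section 10.2 plans no safety analysis, but that has no bearing on whether a dose is held, and QTc is a secondary outcome anyway. These points stand. None supplies a dosing rule.

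The event may be uncommon. Section 2.4 reports similar QTc prolongation with and without methadone in the two adult studies it cites, and the top starting dose is 45 mg/day. Label section 5.4 says cases appear more common above 200 mg/day, but it does not limit them to that range. At lower maintenance doses it names concomitant drugs and hypokalemia as contributors. Appendix 2 offers haloperidol, quetiapine and olanzapine for agitation, and the label lists some neuroleptics as QT-prolonging. A low dose is therefore reassuring but does not settle the matter.

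A reader might also infer that Appendix 2, which suggests considering a higher oral dose when an infusion will not wean, contradicts the label. The documents do not support that. Section 5.1 contains no methadone increase. The label gives a 3 to 5 day interval for pain but allows same-day adjustment in addiction treatment, and neither indication is ICU weaning.

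**Conclusion.** The point holds in this form: the readable protocol gives no on-treatment QTc threshold with a dose action, although it sets entry limits and reads QTc daily. It should be corrected, and the correction is cheap. It is not evidence that the trial is unsafe. Confidence is medium, because the Appendix 5 flow diagram is not shown and Appendix 2's methadone table is broken in the text available. A rule that stands only there cannot be excluded.

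The size is three doses between readings and, at assumed crossing rates of 1% to 10%, a 33% to 98.5% chance that at least one methadone patient meets the situation. The documents give neither a crossing rate nor a relation between methadone exposure and QTc, so no estimate of arrhythmia risk follows from these figures.

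**What to change.** Add to Section 5.1, or to Section 7.4 in place of its present entry:

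> Hold the next methadone dose if the daily QTc is 500 ms or more, or is 60 ms or more above the baseline EKG. Check electrolytes and other QT-prolonging drugs, in line with the label's advice on modifiable risk factors. Cover with infusion or bolus opioid counted in MME. Resume when a later daily reading is below 500 ms and less than 60 ms above baseline. If a routine-care 12-lead EKG is available, use it in place of the monitor value.

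In Appendix 6, record methadone holds and the maximum on-treatment QTc beside the mean. If Appendix 5 already shows a hold step, bring its wording into Section 5.1 and align the limits.

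The limits follow Section 3.4, with one adaptation: the rise is measured from the baseline EKG, whereas the entry rule uses prior EKGs from the same ICU admission.

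The cost is a short amendment, a nurse-training update and two data fields. No extra patients or scheduled tests are needed, though an electrolyte check may be added at a hold if routine care has not supplied one. The downside is some held doses and somewhat more infusion opioid in the methadone arm. Because baseline QTc comes from an EKG and the daily value from a monitor, a few holds may reflect the change of method.

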2.5 Outcomes

a. Primary

Proportion of patients on methadone that get extubated by day number 5 from the date of intubation

b. Secondary

Proportion of patients that develop prolonged QTC after administration of methadone. Others will be ICU length of stay, ICU mortality, hospital length of stay and hospital mortality.

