4.2 Interventions

Pre-intervention period (1 month)

The objective of this period is to standardize the process to improve familiarity to the investigators. Study procedures will be presented to the nurses by oral presentations, printed material, and by email. The information will include detailed explanation of the process of tapering methadone and weaning patients off opiates as stipulated in the study. It will also elaborate more on the process of managing patients that develop clinical opiate withdrawal symptoms.

Intervention period

Following randomization patients will be assigned to the MG or the NG group. For patients randomized to the MG a "non-formulary medication" order will be placed in the electronic medical record to alert nurses to follow the protocol for patients started on Methadone. For those in the NG group usual hospital protocol of weaning opioids will be followed.

The study is completed for each patient once extubated or discharged from ICU, death, comfort care measures, or after 30 days of participation in the study.

We will collect data regarding participants demographic characteristics, comorbidities, main admission diagnosis, use of mechanical ventilation and vasopressors, ICU and hospital LOS, ICU and hospital mortality. Vital signs, focused general examination, LFTs, with normal ICU standard of care will done. However, EKG will be done at baseline and on day 30 if patient is still on methadone. LFTs are only done at baseline. The duration of use of the medication is not expected to cause an increase in LFTs. The listed labs are the only additional labs other than what is usually ordered for standard care in ICU. The information will be collected by reviewing medical records and will be recorded in electronic form only, using REDCap.

#UTHealth Houston

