8.1. Definitions

Serious adverse events include persistent hypotension, persistently prolonged QTc, ileus, anaphylaxis and death.

#UTHealth Houston

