10.2. Statistical and Analytical Plans

Methadone when used at appropriate doses is considered safe and is an FDA approved medication. We will not be performing safety analysis. We will perform interim analysis after randomizing up to 50%(40) patients. Categorial variable will be compared using the student Chisquared test and continuous variables will be compared using the T-test. Interim analysis will be performed by an independent statistician blinded for the treatment allocation. The statistician will report to the data safety and monitoring committee. The DSMB will discuss the results of the interim analysis with the statistician and a steering committee and in a joint meeting will decide on continuation of the trial.

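### The QTc secondary outcome has no threshold and names only methadone patients; defining it and adding a baseline-adjusted mean QTc comparison in both arms would be a cheap improvement

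*Combined protocol and SAP*

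**What the plan says.** - **Outcome (2.5, Secondary):** "Proportion of patients that develop prolonged QTC after administration of methadone". No threshold, measurement source or control-arm counterpart is given.
- **Entry (3.4):** one exclusion is "Patients with prolonged QTc interval ≥500", so a patient reading 499 may enter. A change criterion, "Patients with QTc increase of ≥60 milliseconds above the value of prior EKGs measured during current ICU admission", is also an exclusion. It is not repeated as an on-study event.
- **Adverse events (8):** "These include QTc >500, high grade arrhythmias such as ventricular tachycardia, hypotension and elevated Liver function testing". No repeat reading or change from baseline is asked for.
- **Serious events (8.1):** "Serious adverse events include persistent hypotension, persistently prolonged QTc, ileus, anaphylaxis and death". Persistence is mentioned, but with no number or duration.
- **Measurement (6 and 4.2):** "QTc values will be obtained from patient monitors and documented on data collection tool daily", whereas "EKG will be done at baseline and on day 30 if patient is still on methadone".
- **Analysis (10.2):** "Categorial variable will be compared using the student Chisquared test and continuous variables will be compared using the T-test". The same section says that no safety analysis will be done.
- **Form (Appendix 6):** the tool as shown has one QTc field, the average while on methadone. It shows no baseline, daily or control-arm QTc field.

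**The concern.** QTc is the first-named secondary outcome, yet an analyst could not compute it from the text. The only number available is the adverse-event value in section 8. Used as the outcome definition, it has an awkward property: the event line coincides with the entry line, and each patient is tested against it every day. Someone who enters at 490 needs a fluctuation of just over 10 ms to be counted as having developed prolongation.

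Two things are at stake. First, because the outcome and the form field are worded for methadone patients only, there may be no background rate to set beside the methadone figure. Random crossings could then be read as a drug effect. Second, even with both arms counted, random crossings dilute the contrast, and the unadjusted tests in 10.2 make no use of the baseline EKG that 4.2 collects.

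**Working it through.** **Inputs from the documents.** Entry QTc below 500 (3.4); event above 500 (8); daily readings (6); follow-up of at most 30 days, ending earlier at extubation, ICU discharge, death or comfort care (4.2); 80 patients randomised 1:1 (10.1, 4.1), so 80/2 = 40 per arm. The plan gives no QTc mean, SD or event rate, so it has no QTc figure to reproduce.

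**Assumptions.** True patient QTc is normal, with mean 430-450 ms and between-patient SD 25-30. Each reading, including baseline, adds independent normal error with SD 15-25. Patients enter if the baseline reading is below 500. There are five daily readings. Settings are written mean/between SD/reading SD.

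**Step 1: one patient near the line.** For true QTc 490 and reading SD 20, one reading exceeds 500 with probability 1 - Φ(10/20) = 0.309. Over five readings, 1 - (1 - 0.309)^5 = 84%. With reading SD 10, the single-reading probability is 1 - Φ(10/10) = 0.159 and the five-reading figure is 58%.

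**Step 2: all entrants, no drug effect (simulation).**

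| Setting | Any reading >500 | Two consecutive >500 | Patient mean >500 | Share of any->500 cases who entered at 480-499 |
|---|---|---|---|---|
| 430/25/15 | 2% | 0.3% | 0.2% | 46% |
| 440/30/15 | 6% | 1.5% | 0.9% | 54% |
| 440/30/20 | 10% | 2.1% | 1.2% | 39% |
| 450/30/20 | 16% | 3.8% | 2.2% | 42% |
| 450/30/25 | 22% | 5.0% | 2.8% | 33% |

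The first column depends on the assumptions. With day-to-day error correlation of 0.5 it runs from about 1.7% to 18%. Over a wider grid (mean 430-460, between SD 20-30, reading SD 10-20, 2 to 10 readings) it runs from about 0.1% to 31%. Between 4% and 10% of the simulated cases have a true QTc above 500, so not every case is noise.

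**Step 3: power at 440/30/20, 40 per arm, every methadone patient shifted by +15 ms, two-sided 5%.**

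- *Chi-squared on any reading >500.* The simulated event rates are about 10% and 22%. Pooled p = 0.16, null SE = √(2 × 0.16 × 0.84/40) = 0.082, and alternative SE = √((0.10 × 0.90 + 0.22 × 0.78)/40) = 0.081. Power ≈ Φ((0.12 - 1.96 × 0.082)/0.081) ≈ Φ(-0.50) ≈ 31%. Simulation gives about 30%.
- *t-test on mean QTc.* Given baseline, the variance of the five-reading mean is 900 × 400/1300 + 400/5 = 277 + 80 = 357. Baseline contributes a further (900/1300)² × 1300 × 0.814 = 507, where 0.814 is the variance reduction from truncating baseline at 500. The SD is √864 = 29.4 and the SE is 29.4 × √(2/40) = 6.57. Power ≈ Φ(15/6.57 - 1.96) = Φ(0.32) ≈ 63%. Simulation gives about 61%.
- *Mean QTc adjusted for baseline.* The residual SD is √357 = 18.9 and the SE is 18.9 × √(2/40) = 4.23. Power ≈ Φ(15/4.23 - 1.96) = Φ(1.59) ≈ 94%. Simulation gives about 93%.

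For a uniform +25 ms shift, chi-squared reaches about 71% and the adjusted mean about 100%. With error correlation of 0.5, the +15 ms figures are 28% and 87%.

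**Step 4: does the advantage survive a different pattern of effect?** If 15% of methadone patients rise by 60 ms and the rest do not change (440/30/20), power is 35% for the adjusted mean and 24% for the proportion. At 430/25/15 with 15% rising by 100 ms the order reverses: about 64% against 68%.

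**The case against.** A reader might infer that the protocol will label any single reading above 500 as an outcome case, so that 2-22% of patients will be misclassified. The documents do not support that. Section 2.5 never refers to section 8, and section 8 lists events to chart, not an outcome definition. The only QTc field in Appendix 6 is a patient mean, and 10.2 sends continuous variables to a t-test. A mean-based reading is therefore at least as well supported, and it gives about 0.2-3%. Section 10.2 also disclaims safety analysis, so a chi-squared test on readings above 500 is not actually stated for this outcome.

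A reader might also infer that the proportion would mainly reflect who entered close to 500. Entrants at 480-499 supply 33-54% of simulated cases, more than half in only one of the five settings.

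A third inference is that the proportion should give way to a mean. Step 4 shows why it should not: a mean can hide the few patients with large rises whom a QTc outcome is meant to find.

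It is also fair to say that random crossings affect both arms alike if both are read, so they dilute a randomised comparison and do not bias it. Baseline is an EKG and follow-up a monitor reading, while the calculation treats them as equally precise. A constant offset between the two would fall on both arms and leave the adjusted difference unbiased, but weaker agreement would lower the 93%.

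What stands is that the outcome is undefined, has no stated control-arm counterpart, and is served only by tests that ignore baseline.

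**Conclusion.** This is a cheap improvement to one secondary outcome; it does not affect the primary comparison. It follows from the text alone that the outcome has no threshold, that its wording covers methadone patients only, and that sections 2.5, 6, 8 and 10.2 and Appendix 6 do not fit together on QTc.

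The 2-22% is illustrative. It applies only if the section 8 value is adopted as an any-reading rule, and it rests on the assumed means, SDs, independent errors and five readings. The gain from about 30% or 61% to 93% power holds for a uniform +15 ms shift at 440/30/20. It shrinks or reverses when the effect is concentrated in a few patients. The adjusted mean therefore belongs beside the proportion and should not replace it.

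**What to change.** 1. In 2.5, state what counts as developing prolonged QTc and from which measurement. The choice of value is for the investigators.
2. In 2.5 and 10.2, keep the QTc proportion and report it for both arms, split by baseline QTc and by single versus repeated readings.
3. In 10.2, add the between-arm difference in each patient's mean daily post-randomisation QTc, from a linear model with arm and baseline QTc, with a 95% CI.
4. Reconcile 2.5, 6, 8 and 10.2 and Appendix 6, including the statement that no safety analysis will be done. Add baseline and daily QTc fields for both arms to the form.
5. Leave the charting of events in section 8 and all patient management unchanged.

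The cost is a few extra form fields and one more analysis. Sections 4.2 and 6 already call for the baseline EKG and the daily readings, but collection in the control arm should be made explicit.

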2.3. Secondary Objectives

To assess the safety of methadone administration in critically ill patients while in the hospital.

To determine hospital length of stay from the time of enrollment to the time of discharge

2.4. Potential Risks and Benefits:

a. End Points – Efficacy

The study might show the efficacy and potency of methadone in decreasing the length of stay in ICU and duration of mechanically intubation in critically ill patients.

b. End Points - Safety

Adverse events that could be anticipated during the study include signs of opioid withdrawal, elevated liver enzymes, ileus, hypotension and QTC prolongation. Adverse events will be reported in the adverse events registry.

The only two adult studies reported on the use of methadone to wean opioids on mechanical ventilation showed that the much-anticipated risk of QTC prolongation was similar in both patients who received methadone and those that did not receive methadone as shown in the study by Wanzuita et al and Al-Qadheeb et al. [5] Methadone was well tolerated in both studies.

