Bone or Joint aches If patient was having pain previously, only the additional component attributed to opiates withdrawal is scored O not present mild diffuse discomfort patient reports severe diffuse aching of joints/muscles patient is rubbing joints or muscles and is unable to sit still because of discomfort	Gooseflesh skin 0 skin is smooth 3 piloerrection of skin can be felt or hairs standing up on arms 5 prominent piloerrection			
Runny nose or tearing Not accounted for by cold symptoms or allergies 0 not present 1 nasal stuffiness or unusually moist eyes 2 nose running or tearing 4 nose constantly running or tears streaming down cheeks	Total Score The total score is the sum of all 11 items Initials of person completing assessment:			

Score: 5-12 = mild; 13-24 = moderate; 25-36 = moderately severe; more than 36 = severe withdrawal This version may be copied and used clinically.

Journal of Psychoactive Drugs

[figure not shown]
Volume 35 (2), April - June 2003

Source: Wesson, D. R., & Ling, W. (2003). The Clinical Opiate Withdrawal Scale (COWS). J Psychoactive Drugs, 35(2), 253–9.

Appendix 5

Protocol Flow

Appendix 6

#UTHealth Houston

Data Collection Tool

Patient Identification Code (MRN):

Baseline Characteristics Age (years) Sex		
Sex		
Race		
Weight (Kg)		
Duration on ventilator at time of		
randomization (Hours)		
	Pneumonia = 1	
, , ,	Aspiration = 2	
	Non-Pulmonary Sepsis = 3	
	COPD Exacerbation = 4	
	Other Causes = 5	
Assessments and Measurements	Other Causes - 5	
APACHE II Score		
Total SOFA Score		
Tidal Volume ml/kg of predicted		
body weight		
Peep at time of enrollment (cm H2O)		
PaO2: FIO2 ratio (mmHg)		
FiO2 at time of enrollment		
Duration on mechanical ventilation		
before start of weaning(hours)		
Last recorded Ph prior to enrollment		
Duration in ICU stay after enrollment		
(Hours)		
Mean QTc while on Methadone		
Clinical Opiate Withdrawal Scale		
(COWS) after extubation		
Adverse Event		
Medication Parameters		
Fentanyl Initial Dose (mcg/hour)		
Fentanyl accumulated dose(mcg)		
Days on Fentanyl before start of		
weaning		
Hydromorphone initial Dose		
(mg/hour)		
Hydromorphone accumulated		
dose(mg)		
Days on Hydromorphone before		
start of weaning		
Dexmedetomidine accumulated		
dose(mcg)		
Midazolam accumulated dose(mg)		
Propofol accumulated dose (mg)		
Ketamine accumulated dose (mg)

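### The only visible QTc field, a mean on methadone, cannot yield the planned QTc outcome, and the ≥60 ms rise that bars entry is not a listed on-study event

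*Combined protocol and SAP*

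**What the plan says.** **Entry (section 3.4).** Two QTc rules exclude a patient: an absolute one, "Patients with prolonged QTc interval ≥500", and a change rule, "Patients with QTc increase of ≥60 milliseconds above the value of prior EKGs measured during current ICU admission".

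**On study (sections 8 and 8.1).** Adverse events are to be charted: "These include QTc >500, high grade arrhythmias such as ventricular tachycardia, hypotension". Raised liver tests complete the list. Section 8.1 makes persistent QTc prolongation a serious event, without a value or a duration.

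**Outcome (section 2.5).** The first secondary outcome is "Proportion of patients that develop prolonged QTC after administration of methadone". No cut-off is given and the control arm is not mentioned.

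**Data (sections 4.2 and 6, Appendix 6).** Section 6 says "QTc values will be obtained from patient monitors and documented on data collection tool daily", with no restriction by arm. Section 4.2 schedules an EKG at baseline, and another on day 30 only for a patient still taking methadone. The visible Appendix 6 sheet has one QTc field, "Mean QTc while on Methadone", and a general adverse event field.

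**Analysis (sections 2.3 and 10.2).** Section 2.3 lists the safety of methadone as a secondary objective. Section 10.2 names a chi-squared test for categorical variables, but also states "We will not be performing safety analysis".

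**The concern.** The outcome, the form and the analysis text do not fit together. The outcome counts patients whose QTc became prolonged. The visible field averages QTc over methadone exposure. The analysis section both provides a test for categorical variables and rules out a safety analysis. If data were collected as the sheet shows, the QTc outcome could not be derived from its QTc field, and prolongation from other causes in ICU patients could not be set against a control rate. That comparison matters to the plan's own argument: section 2.4 relies on earlier studies in which the "risk of QTC prolongation was similar in both patients who received methadone and those that did not receive methadone".

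The second issue is patient safety. The plan treats a rise of ≥60 ms as enough to keep a patient off the study. After enrolment, while the patient is taking methadone, the same rise is not a listed event unless the reading also passes 500.

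**Working it through.** The plan gives no QTc rate, variance or power figure, so there is nothing of its own to reproduce on this point. Its only number used here is the total of 80 patients allocated 1:1 (sections 4.1 and 10.1), so 80 / 2 = 40 per arm.

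**1. Can the outcome be derived from the mean field?** Assume a baseline of 400 ms, one day at 470 ms and all other days at 410 ms. These readings are illustrative and do not come from the documents.

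- 3 days: (470 + 2 × 410) / 3 = 430 ms, recorded as +30 over baseline
- 5 days: (470 + 4 × 410) / 5 = 422 ms, recorded as +22
- 10 days: (470 + 9 × 410) / 10 = 416 ms, recorded as +16

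The actual peak was 470 − 400 = +70 ms in each case. A patient with 430 ms on all three days has the same 3-day mean but a peak rise of only 30 ms. The mean therefore does not determine who crossed a limit. A control patient has no methadone exposure, so the field is empty for that arm.

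**2. Where does the ≥60 ms gap lie?** The listed event requires a reading above 500. A rise of at least 60 ms escapes it when baseline + 60 ≤ 500, that is, when baseline ≤ 500 − 60 = 440 ms. The largest rise that escapes is 500 − baseline.

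| Baseline (ms, illustrative) | After a 60 ms rise | Above 500? | Rises of ≥60 ms meeting no stated numeric limit |
|---|---|---|---|
| 380 | 440 | no | 60 to 120 |
| 400 | 460 | no | 60 to 100 |
| 420 | 480 | no | 60 to 80 |
| 440 | 500 | no | 60 only |
| 441 | 501 | yes | none |

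From 441 ms upward the existing limit catches every such rise. There is also a small boundary mismatch: a reading of exactly 500 bars entry but is not a listed event on study.

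**3. How precise would a between-arm comparison be?** The 95% half-width on the difference is 1.96 × √[p₁(1 − p₁)/40 + p₂(1 − p₂)/40]. The event rates are assumed.

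- 5% v 5%: 1.96 × √(0.0475/40 + 0.0475/40) = 9.6 points
- 10% v 5%: 1.96 × √(0.09/40 + 0.0475/40) = 11.5 points
- 20% v 10%: 1.96 × √(0.16/40 + 0.09/40) = 15.5 points

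These are normal approximations and are rough at low rates (5% of 40 is 2 events). They show that the comparison can only be descriptive.

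**The case against.** A reader might infer that QTc is to be assessed in the methadone arm alone. The documents do not support that. The primary outcome in section 2.5 is also worded for patients on methadone, yet sections 6 and 10.1 compare it between arms, at 50% v 20%. Sections 6.1 and 7.5 blind the assessors of primary and secondary outcomes to group, which makes sense only if both arms are assessed. Daily QTc in section 6 is not limited to one arm. The visible Appendix 6 sheet also lacks other planned items, such as mortality, so it is not the full data set, and its adverse event field could hold a reading above 500. This objection stands: the text conflicts with itself, and it does not prove that no comparison is intended.

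Entry limits and event limits also serve different purposes and need not match. The entry rule compares EKGs, while on-study values come from monitors. The section 8 list is open-ended, and the serious event in 8.1 has no floor of 500, so a clinician could report a large rise that stays below 500. That also stands. What is missing is a stated numeric limit for such a rise.

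Finally, a reader might infer that the plan has no route from a QTc value to a decision on a patient's methadone. No visible text sets one, but the Appendix 5 flow diagram is not shown and could contain it. Section 7.3 warns against use in QT prolongation, the label in Appendix 3 allows dose reduction after unacceptable adverse reactions, and under section 8.2 the principal investigator evaluates adverse events. A gap here is not demonstrated.

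**Conclusion.** The point holds in limited form and is minor to moderate. The only visible QTc field cannot produce the section 2.5 proportion and has no control-arm value. Sections 6 and 10.2 leave it unclear whether the arms will be compared. The absolute 500 level is carried into the study, with a slightly different boundary, but the ≥60 ms rise is not. The resulting gap is confined to baselines of 440 ms or less.

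Two limits apply. The documents give no QTc distribution, so the number of patients affected cannot be estimated. The conclusion about the form rests on the visible part of Appendix 6; a fuller electronic form with daily values in both arms would remove the data-capture issue, leaving the event definition and the section 10.2 sentence to correct.

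**What to change.** 1. **Appendix 6.** Replace the mean field with baseline and daily (or maximum) monitor QTc in both arms, in line with section 6. Take the baseline from the monitor, so that change is measured on one instrument.
2. **Sections 2.5 and 8.** Define the QTc event as ≥500 ms, or ≥60 ms above the monitor baseline. Report the proportion in each arm from randomisation to the patient's study end in section 4.2, as a descriptive comparison. Give the number of reading days per arm, because follow-up can end at extubation and the arms are expected to differ on that.
3. **Section 10.2.** Amend the sentence that rules out a safety analysis to match.

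A statement linking these limits to a documented decision on continuing, holding or stopping methadone would be a useful optional clarification. Its content is for the investigators and the DSMB.

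**Cost.** A short amendment and a small form change, with no new test. Added entry is at most 80 baseline values plus 40 × 30 = 1,200 control-arm daily values. If only the maximum is kept, the 1,200 falls to 40. It is less still if section 6 already covers both arms. The downsides are more reported QTc events and the wide intervals shown above.
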